4.1.3 Arm 2 Part II: Cohort Expansion in Metastatic Visceral Lesion Tumors

Arm 2 Part II supports the visceral cohort expansion phase, which will enroll 30 participants (or less due to early study termination) into each of the below cohorts:

Cohort D: Hepatocellular carcinoma

Cohort E: Gastric carcinoma

V937 will be administered at the RP2D (defined in Arm 2 Part I). V937 will remain at a constant dose administered ITu on Days 1 and 8 of Cycle 1 (28 days), then Day 1 of Cycle 2 through Cycle 8, for a maximum of 9 doses. The dose of pembrolizumab will remain constant at 200 mg IV every 21 days for a maximum of 35 treatment cycles (approximately 2 years).

Specific procedures to be performed during the study, as well as their prescribed times and associated visit windows, are outlined in the SoA in Section 1.3. Details of each procedure are provided in Section 8.

4.2 Scientific Rationale for Study Design

This study design is a two-arm, non-randomized, open-label study of ITu V937 + pembrolizumab IV in participants with advanced/metastatic solid tumors who have not received prior therapy with anti-PD-1/PD-L1 agents, T-VEC, or other oncolytic virus therapies.

V937 infects both normal and tumor cells by binding to ICAM-1, a viral cell surface receptor reported to be overexpressed in many different tumor types. Upon successful entry into a tumor cell, oncolytic viruses leverage a tumor cell's abnormal response to cell signaling, homeostasis, and stress in order to propagate an infection, which ultimately leads to cell lysis. Once lysis occurs, a cascade of events occurs involving the release of tumor-associated antigens as well as recruitment of antigen-presenting and cytotoxic T cells to the tumor site to affect an anti-tumor response [Krishnamurthy, S., et al 2006] [Stojdl, D. F., et al 2000].

4.2.1 Rationale for Endpoints

4.2.1.1 Efficacy Endpoints

Depending on the trial arm, the primary endpoints in this study include: OR (Arm 1) and DLT, AE and discontinuation of study intervention due to AE (Arm 2 Parts I and II). Secondary endpoints include PFS, DOR, OR by iRECIST and OS for Arm 1, and ORR by RECIST 1.1 and iRECIST for Arm 2 Part II. ORR is the proportion of participants with OR.

Tumor response will be assessed using RECIST 1.1 and iRECIST as assessed by investigator (see Section 8.2.1). Antitumor activity will be measured through such endpoints as the OR, PFS, and OS, which are described further in Section 9.4.1. A planned interim futility analysis is described in Section 9.7.

This study will assess ORR based on RECIST 1.1 criteria as determined by the investigator. Objective response rate is an acceptable measure of clinical benefit that demonstrates superiority of a new antineoplastic therapy, especially if the magnitude of the effect is large and the therapy has an acceptable risk/benefit profile. The use of RECIST 1.1 to assess ORR is typically considered acceptable by regulatory authorities.

RECIST 1.1 will be used for efficacy measures as assessed by the investigator when determining eligibility (Section 8.2.1). Although traditional RECIST 1.1 references a maximum of 5 target lesions in total and 2 per organ, this protocol has implemented a modification to RECIST 1.1 to allow for a maximum of 10 target lesions in total and 5 per organ. Furthermore, because ITu therapy is included by design in this study, RECIST 1.1 is also modified to specify that ITu injection itself does not render a lesion non-evaluable.

RECIST 1.1 will be adapted to account for the unique tumor response characteristics seen following treatment with pembrolizumab (iRECIST, Section 8.2.5). Immunotherapeutic agents such as pembrolizumab may produce antitumor effects by potentiating endogenous cancer-specific immune responses. The response patterns seen with such an approach may extend beyond the typical time course of responses seen with cytotoxic agents, and participants treated with pembrolizumab may manifest a clinical response after an initial increase in tumor burden or even the appearance of new lesions. Thus, standard RECIST 1.1 may not provide an accurate response assessment of immunotherapeutic agents such as pembrolizumab. Based on an analysis of participants with melanoma enrolled in KEYNOTE-001 (KN001), 7% of evaluable participants experienced delayed or early tumor pseudo-progression. Of note, participants who had PD by RECIST 1.1, but not by the immune-related response criteria [Wolchok, J. D., et al 2009] had longer overall survival than participants with PD by both criteria [Hodi, F. S., et al 2014]. Additionally, the data suggest that RECIST 1.1 may underestimate the benefit of pembrolizumab in approximately 15% of participants. These findings support the need to apply a modification to RECIST 1.1 that takes into account the unique patterns of atypical responses in immunotherapy and enables treatment beyond initial radiographic progression, if the participant is clinically stable.

Modified iRECIST assessment has been developed and published by the RECIST Working Group, with input from leading experts from industry and academia, along with participation from the US FDA and the EMA [Seymour, L., et al 2017]. The unidimensional measurement of target lesions, qualitative assessment of nontarget lesions, and response categories are identical to RECIST 1.1, until progression is seen by RECIST 1.1. However, if a participant is clinically stable, additional imaging may be performed to confirm radiographic progression. iRECIST will be used by investigators to assess tumor response and progression and make treatment decisions.

For further information on iRECIST, see Section 8.2.5.

4.2.1.1.1 Response Rate Assessed by RECIST Version 1.1

RECIST 1.1 will be used to determine the objective response. Although traditional RECIST 1.1 references a maximum of 5 target lesions in total and 2 per organ, this protocol has implemented a modification to RECIST 1.1 to allow a maximum of 10 target lesions in total and 5 per organ. Furthermore, because ITu therapy is included by design in the study, RECIST 1.1 is also modified to specify that ITu injection itself does not render a lesion non-evaluable.

4.2.1.2 Safety Endpoints

In Arm 1, safety and tolerability of ITu V937 in combination with pembrolizumab is a secondary objective. In Arm 2, safety and tolerability of ITu V937 in combination with pembrolizumab is a primary objective. The primary safety analysis will be based on participants who experience toxicities as defined by NCI CTCAE v5.0 criteria. Safety will be assessed by quantifying the types and grades of toxicities experienced by participants who have received V937 in combination with pembrolizumab.

For AEs, attribution to drug, time-of-onset, duration of the event, its resolution, and any concomitant medications administered will be recorded. Adverse events that will be analyzed include, but are not limited to, DLTs, AEs, SAEs, fatal AEs, and laboratory changes.

4.2.1.3 Pharmacokinetic Endpoints

A tertiary/exploratory objective of this study is to characterize the PK profile of V937 following ITu administration in combination with pembrolizumab. The serum concentrations of these agents will serve as the primary readout for the PK, and these data will be used to derive PK parameters of V937. Furthermore, the results of these analyses will be used in conjunction with the pharmacodynamics, and safety and exploratory endpoint data to help assess future dosing strategies for V937.

4.2.1.4 Pharmacodynamic Endpoints

4.2.1.4.1 Neutralizing V937 Antibodies

Neutralizing antibody responses at the beginning of each cycle will be determined to understand drug exposure and safety. The incidence of neutralizing antibodies will be evaluated and summarized over time. Correlations between the presence/absence of positivity for neutralizing antibodies, PK and pharmacodynamic markers, activity, and safety of V937 will be explored.

4.2.1.5 Planned Exploratory Biomarker Research

Cancer immunotherapies represent an important and novel class of antitumor agents. However, the mechanism of action of these exciting new therapies is not completely understood and much remains to be learned regarding how best to leverage these new drugs in treating patients. Thus, to aid future patients, it is important to investigate the determinants

of response or resistance to cancer immunotherapy and other treatments administered, as well as determinants of AEs in the course of our clinical studies. These efforts may identify novel predictive/PD biomarkers and generate information that may better guide single-agent and combination therapy with immuno-oncology drugs. To identify novel biomarkers, biospecimens (ie, blood components, tumor material) will be collected to support analyses of cellular components (eg, protein, DNA, RNA, metabolites) and other circulating molecules. Investigations may include but are not limited to:

CCI

C1

4.2.1.6 Future Biomedical Research

The Sponsor will conduct future biomedical research on specimens for which consent was provided during this study. This research may include genetic analyses (DNA), gene expression profiling (RNA), proteomics, metabolomics (serum, plasma), and/or the measurement of other analytes, depending on which specimens are consented for future biomedical research.

Such research is for biomarker testing to address emergent questions not described elsewhere in the protocol (as part of the main study) and will only be conducted on specimens from appropriately consented participants. The objective of collecting/retaining specimens for future biomedical research is to explore and identify biomarkers that inform the scientific understanding of diseases and/or their therapeutic treatments. The overarching goal is to use such information to develop safer, more effective drugs/vaccines, and/or to ensure that participants receive the correct dose of the correct drug/vaccine at the correct time. The details of future biomedical research are presented in Appendix 6.

4.3 Justification for Dose

4.3.1 Starting Dose for This Study

4.3.1.1 Rationale for Starting and Maximum Dose of V937

Participants with Subcutaneous Tumors (V937 3 × 10⁸ TCID₅₀, ITu + Pembrolizumab 200 mg IV)

The clinical development of V937 has included safety and efficacy assessments using 3 different routes of administration: ITu, intravesical, and IV. ^{CCI} [REDACTED]

The ITu dose for this study comes from Phase 2 studies conducted in participants with advanced melanoma (CALM and CAPRA). In the CALM study, late-stage melanoma participants were treated with V937 at a maximum dose of 3×10^8 TCID₅₀ and showed an ORR of 28%. Furthermore, in the CAPRA study, late-stage melanoma participants were treated with V937 at a dose of 3×10^8 TCID₅₀ in combination with pembrolizumab and showed an ORR of 59% [Pandha, H. S. 2018]. Evidence for biological activity and tolerability in the CALM and CAPRA studies supported moving forward with 3×10^8 TCID₅₀ RP2D in this study.

The dosing schedule in this study for ITu administration in Arm 1 is based on the CAPRA study. A maximum total dose of 3×10^8 TCID₅₀ will be administered on Days 1, 3, 5, 8, of Cycle 1, then every 3 weeks (Cycles 2-8) for a total of 11 doses.

The dose for pembrolizumab is 200 mg IV every 3 weeks. The pembrolizumab dose and schedule is identical to that used in the CAPRA study, which is based on the current SOC.

Please refer to the V937 IB for additional information regarding dose selection.

Participants with Visceral Tumors (V937 Dose Escalation and Cohort Expansion, ITu + Pembrolizumab 200 mg IV)

Injection into visceral tumors has not previously been tested with V937. Therefore, this regimen will employ dose escalation to determine the RP2D for visceral injections. Injection into visceral tumors is technically challenging compared to subcutaneous injections. Therefore, frequency of injections is limited to once-per-week.

V937 doses will be escalated at three different dose levels: 3×10^7 TCID₅₀; 1×10^8 TCID₅₀, and; 3×10^8 TCID₅₀. The total administered dose is dependent on the tumor size (see [Table 11](#) and [Table 13](#)). The maximum injected doses for DL1, DL2 and DL3 of V937 will be 3×10^7 TCID₅₀, 1×10^8 TCID₅₀, and then 3×10^8 TCID₅₀. V937 is administered on

[figure not shown]
Day 1 and Day 8 of Cycle 1, and Day 1 of Cycles 2-8 for a total of 9 doses. The initial dose escalation will occur in all-comer tumors metastatic to liver. Note that injections will be direct into metastatic liver lesions, and NOT hepatic intraarterial injections. Multiple tumor histologies will be allowed in the visceral dose escalation cohort (including, but not limited to: NSCLC, CRC, and pancreatic carcinomas). After reaching a RP2D using the mTPI dose escalation scheme derived from Arm 2 Part I cohort, the trial will subsequently expand into 2 additional visceral tumor cohorts, HCC (Cohort D) and gastric carcinoma (Cohort E). These visceral cohorts will begin enrolling approximately 12 to 18 months following the completion of Arm 1 Part I dose escalation.

The dose for pembrolizumab is 200 mg IV every 3 weeks, which is based on the current SOC.

[figure not shown]
4.3.1.2 Rationale for Dose Interval and Escalation Increments

The starting dose and dose interval of V937 is based on integrating nonclinical toxicological, pharmacological, and efficacy data. Dose finding will proceed CCI

CCI

CCI

CCI

4.4 Beginning and End of Study Definition

The overall study begins when the first participant signs the ICF. The overall study ends when the last participant completes the last study-related telephone-call or visit, withdraws from the study, or is lost to follow-up (ie, the participant is unable to be contacted by the investigator).

4.4.1 Clinical Criteria for Early Study Termination

Recruitment in the study or at a study site(s) may be stopped due to insufficient compliance with the protocol, GCP and/or other applicable regulatory requirements, procedure-related problems or the number of discontinuations for administrative reasons is too high.

Early study termination will be the result of the criteria specified below:

1. If the incidence and/or severity of adverse drug reactions or procedure-related complications suggest that the risk/benefit ratio is unfavorable to participant
2. If the incidence and/or severity of emerging effects/clinical endpoints suggest that the risk/benefit ratio to the study population is unacceptable
3. If there are plans to either modify or discontinue development of study drug

Ample notification will be provided if Sponsor decides to terminate the supply of V937 or pembrolizumab.

Upon study completion or early study termination, participants who have completed or discontinued V937 treatment and are only receiving pembrolizumab may be enrolled in a pembrolizumab extension study, if available, to continue pembrolizumab monotherapy for up to 35 cycles from first pembrolizumab dose on V937-013.

5 STUDY POPULATION

Male and Female participants at least 18 years of age with advanced/metastatic solid tumors will be enrolled in this study. (See Appendix 7 for country-specific requirements.)

Prospective approval of protocol deviations to recruitment and enrollment criteria, also known as protocol waivers or exemptions, is not permitted.

5.1 Inclusion Criteria

A participant will be eligible for inclusion in the study if the participant:

5.1.1 Overall Inclusion Criteria

1. Has locally-advanced disease that is not amenable to surgery or radiation, or Stage IV advanced/metastatic solid tumor malignancies.

Note: Tumor-specific criteria are provided in Section 5.1.2.1 (TNBC), Section 5.1.2.2 (HNSCC), Section 5.1.2.3 (cSCC), Section 5.1.3 (Visceral lesion dose escalation), Section 5.1.4.1. (HCC), and Section 5.1.4.2 (Gastric).

2. Has histologically- or cytologically-confirmed diagnosis of an advanced/metastatic solid tumor.
3. Has measurable disease by RECIST 1.1 criteria as assessed by investigator. Target lesions in a previously irradiated area will be considered measurable if progression has been demonstrated in such lesions.
4. Has submitted a baseline tumor sample for analysis (either *de novo* biopsy or an archival tumor block). For details on tumor tissue submission, see the Procedures Manual.

Note: Arm 2 Part I: If tissue block is not available, participant may be enrolled if all other inclusion criteria are satisfied.

5. Has a performance status of 0 or 1 on the ECOG Performance Scale obtained within 72 hours prior to the first dose of study intervention.
6. If participants have known HIV-positive disease, participants must have well-controlled HIV on ART defined as:
 - a. CD4+ T-cell count >350 cells/mm³ at the time of screening.
 - b. Must have achieved and maintained virologic suppression, defined as HIV RNA levels below 50, or LLOQ (below limits of detection), using a locally available assay at the time of screening.
 - c. Must be on a stable regimen without any changes in drugs or dose modifications for a minimum of 4 weeks prior to study entry (Day 1) [Uldrick, T. S., et al 2019].

7. Demonstrate adequate organ function as defined in [Table 7](#). These laboratory samples must be collected within 72 hours prior to the first dose of study intervention.

Table 7 Adequate Organ Function Laboratory Values for Non-HCC Population

System	Laboratory Value
Hematological	
Absolute neutrophil count	>1,500/mcL
Platelets	>100,000/mcL
Hemoglobin	≥8 g/dL or >5.6 mmol/L ^a
Renal	
Creatinine OR Measured or calculated ^b CrCl (GFR can also be used in place of CrCl)	≤1.5 × ULN or ≥30 mL/min for participants with creatinine levels >1.5 × ULN
Hepatic	
Total bilirubin (serum)	≤1.5 × ULN or Direct bilirubin ≤ULN for participants with total bilirubin levels >1.5 × ULN
AST (SGOT) and ALT (SGPT)	<2.5 × ULN or ≤5 × ULN for participants with liver metastases
Coagulation	
International Normalized Ratio (INR) or Prothrombin Time (PT) Activated Partial Thromboplastin Time (aPTT)	<1.5 × ULN (unless participant is receiving anticoagulant therapy, in which case PT/INR or aPTT should be within the therapeutic range of intended use of anticoagulants)

Abbreviations: aPTT=activated partial thromboplastin time; ALT (SGPT) = alanine aminotransferase (serum glutamic pyruvic transaminase); AST (SGOT) = aspartate aminotransferase (serum glutamic oxaloacetic transaminase); CrCl=creatinine clearance; GFR = glomerular filtration rate; INR=International Normalized Ratio; PT=prothrombin time; ULN = upper limit of normal.
 
^a Criteria must be met without packed red blood cell (pRBC) transfusion within the prior 2 weeks. Participants can be on stable dose of erythropoietin (≥ approximately 3 months).
 
^b Creatinine clearance (CrCl) should be calculated per institutional standard.
 
Note: This table includes eligibility-defining laboratory value requirements for treatment; laboratory value requirements should be adapted according to local regulations and guidelines for the administration of specific chemotherapies.
	

Refer to Section 5.1.4.1 for laboratory value requirements for the HCC population.

Demographics

8. Is male or female, from ≥ 18 years of age inclusive, at the time of signing the informed consent.

Male Participants

Contraceptive use by men should be consistent with local regulations regarding the methods of contraception for those participating in clinical studies.

9. Male participants are eligible to participate if they agree to the following during the intervention period for and for at least 120 days after the last dose of study intervention:

PLUS either:

- Be abstinent from heterosexual intercourse as their preferred and usual lifestyle (abstinent on a long term and persistent basis) and agree to remain abstinent

OR

- Must agree to use contraception unless confirmed to be azoospermic (vasectomized or secondary to medical cause [Appendix 5]) as detailed below:

Agree to use a male condom plus partner use of an additional contraceptive method when having penile-vaginal intercourse with a WOCBP who is not currently pregnant. Note: Men with a pregnant or breastfeeding partner must agree to remain abstinent from penile-vaginal intercourse or use a male condom during each episode of penile-vaginal penetration.

Note: For male participants on pembrolizumab only, no contraception measures are needed.

Female Participants

Contraceptive use by women should be consistent with local regulations regarding the methods of contraception for those participating in clinical studies.

10. A female participant is eligible to participate if she is not pregnant or breastfeeding, and at least one of the following conditions applies:

- Is not a WOCBP

OR

- Is a WOCBP and using a contraceptive method that is highly effective (with a failure rate of $<1\%$ per year), or be abstinent from heterosexual intercourse as their preferred and usual lifestyle (abstinent on a long term and persistent basis), as described in Appendix 5, during the intervention period and for at least 120 days after the last dose of study

intervention. The investigator should evaluate the potential for contraceptive method failure (ie, noncompliance, recently initiated) in relationship to the first dose of study intervention.

- A WOCBP must have a negative highly sensitive pregnancy test (urine or serum as required by local regulations) within 72 hours before the first dose of study intervention.
- If a urine test cannot be confirmed as negative (eg, an ambiguous result), a serum pregnancy test is required. In such cases, the participant must be excluded from participation if the serum pregnancy result is positive.
- Additional requirements for pregnancy testing during and after study intervention are located in Appendix 2.
- The investigator is responsible for review of medical history, menstrual history, and recent sexual activity to decrease the risk for inclusion of a woman with an early undetected pregnancy.
- Contraceptive use by women should be consistent with local regulations regarding the methods of contraception for those participating in clinical studies.

Informed Consent

11. The participant (or legally acceptable representative) provides documented informed consent for the study. The participant may also provide consent for future biomedical research. However, the participant may participate in the main study without participating in future biomedical research.

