 - a. Controlled (treated) hepatitis B participants will be allowed if they meet the following criteria: Antiviral therapy for HBV must have been given for a minimum of 12 weeks. HBV viral load must be less than 100 IU/mL prior to first dose of study intervention. **Participants on active HBV therapy with viral loads under 100 IU/mL should stay on the same therapy throughout study treatment.**
 - b. Participants who are anti-HBc (+), negative for HBsAg, negative or positive for anti-HBs, and who have an HBV viral load under 100 IU/mL, do not require HBV anti-viral prophylaxis.

Refer to Section 5.1.3 for visceral lesion dose expansion inclusion criteria.

Refer to Section 5.1.1 for additional inclusion criteria that apply to all tumor cohorts.

30. Demonstrate adequate organ function as defined in [Table 8](#). These laboratory samples must be collected within 72 hours prior to the first dose of study intervention.

Table 8 Adequate Organ Function Laboratory Values for HCC Population

System	Laboratory Value
Hematological	
Absolute neutrophil count	>1,200/mcL
Platelets	>60,000/mcL
Hemoglobin	≥8 g/dL without transfusion or EPO dependency within 7 days.
Renal	
Creatinine OR Measured or calculated ^a CrCl (GFR can also be used in place of CrCl)	≤1.5 × ULN or ≥30 mL/min for participants with creatinine levels >1.5 × ULN ≥60 mL/min required prior to CT fluoroscopy guided injections
Hepatic	
Total bilirubin	≤2 mg/dL or Direct bilirubin ≤ULN for participants with total bilirubin levels >2 mg/dL
AST (SGOT) and ALT (SGPT)	≤5 × ULN
Albumin	≥3.0 g/dL Note: No albumin supplement (or BCAA) allowed within the last 14 days.
Coagulation	
International Normalized Ratio (INR) or Prothrombin Time (PT) Activated Partial Thromboplastin Time (aPTT)	<1.5 × ULN (unless participant is receiving anticoagulant therapy, in which case PT/INR or aPTT should be within the therapeutic range of intended use of anticoagulants)
Abbreviations: ALT (SGPT) = alanine aminotransferase (serum glutamic pyruvic transaminase); aPTT=activated partial thromboplastin time; AST (SGOT) = aspartate aminotransferase (serum glutamic oxaloacetic transaminase); BCAA=branched-chain amino acids; CrCl=creatinine clearance; CT=computed tomography; EPO=erythropoietin; GFR = glomerular filtration rate; INR=International Normalized Ratio; PT=prothrombin time; ULN = upper limit of normal.	
^a Creatinine clearance (CrCl) should be calculated per institutional standard.	

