10.2 Appendix 2: Clinical Laboratory Tests

See Appendix 7 for country-specific requirements.

- The tests detailed in [Table 21](#) will be performed by the local laboratory.
- Protocol-specific requirements for inclusion or exclusion of participants are detailed in Section 5 of the protocol.
- Additional tests may be performed at any time during the study as determined necessary by the investigator or required by local regulations.
- Pregnancy testing:
 - Pregnancy testing requirements for study inclusion are described in Section 5.1.
 - Pregnancy testing (urine or serum as required by local regulations) should be conducted at the end of relevant systemic exposure and correspond with the time frame for female participant contraception in Section 5.1.
 - Additional serum or urine pregnancy tests may be performed, as determined necessary by the investigator or required by local regulation, to establish the absence of pregnancy at any time during the subject's participation in the study.

Table 21 Protocol-required Safety Laboratory Assessments

Hematology	Comprehensive Chemistry Panel	Other
Hematocrit	Albumin	Pregnancy test (serum or urine) ^a
Hemoglobin	Alkaline phosphatase	
Platelet count	Alanine aminotransferase	
WBC (total and differential) ^c	Aspartate aminotransferase	Total T3 (or Free T3 [FT3]), Total T4 (or Free T4 [FT4]), and TSH ^b
	Bicarbonate	
RBC	Calcium	Anti-HCV
Absolute lymphocyte Count ^c	Chloride	HCV viral load
	Creatinine	HCV genotype
Absolute neutrophil Count ^c	Glucose	anti-HBs
	Phosphorus	HBsAg
PT/INR	Potassium	anti-HBc (total and IgM)
aPTT or PTT	Sodium	HBeAg
	Total bilirubin	anti-HBe
	Direct bilirubin	HBV viral load
	Total protein	Anti-HDV
	Blood urea nitrogen (or Urea) ^d	AFP
		CD4+ T-cell count ^e
		GGT (for HECl assessment only)

Abbreviations: AFP=alpha-fetoprotein; aPTT=activated partial thromboplastin time; FT3= Free T3; FT4=Free T4; GGT=gamma glutamyl transpeptidase; HBc=hepatitis B core; HBeAg=hepatitis B e antigen; HBsAg=hepatitis B surface antigen; HBV=hepatitis B virus; HCV=hepatitis C virus; HDV= hepatitis delta virus; HECl= Hepatic Events of Clinical Interest; HIV=human immunodeficiency virus; IgM=immunoglobulin M; PTT=partial thromboplastin time; RBC=red blood cell; T3=triiodothyronine; T4=thyroxine; TSH=thyroid-stimulating hormone; WBC=white blood cell.

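### The two haemoglobin limits in Table 7 (8 g/dL and 5.6 mmol/L) are about 1 g/dL apart, so the non-HCC entry criterion does not state one threshold

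*Combined protocol and SAP*

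**What the plan says.** Inclusion criterion 7 (Section 5.1.1) is mandatory: "Demonstrate adequate organ function as defined in" Table 7, which is headed for the non-HCC population. The haemoglobin row of that table reads ≥8 "g/dL or >5.6 mmol/L".

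Two notes bear on the row, and neither deals with units. Footnote a concerns transfusion and erythropoietin: "Criteria must be met without packed red blood cell (pRBC) transfusion within the prior 2 weeks". The general note under the table says that "laboratory value requirements should be adapted according to local regulations and guidelines for the administration of specific chemotherapies".

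The HCC cohort has its own Table 8 (Section 5.1.4.1), where the row reads "≥8 g/dL without transfusion or EPO dependency within 7 days", with no mmol/L value.

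Three other statements matter for how the limit is applied. Section 4.1 describes a multicentre study run worldwide. Appendix 2 (Section 10.2) says that the Table 21 tests, which include haemoglobin, "will be performed by the local laboratory". Section 5 states: "Prospective approval of protocol deviations to recruitment and enrollment criteria, also known as protocol waivers or exemptions, is not permitted".

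**The concern.** A limit printed in two units should be one threshold written twice, so that the reporting unit of the laboratory makes no difference to who can enter. Here the mmol/L figure looks too high for the g/dL figure, or the g/dL figure too low for the mmol/L figure.

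If so, two candidates with the same haemoglobin could be classified differently according to the unit on the laboratory report. A participant already enrolled could likewise be recorded as eligible or as an eligibility deviation for the same reason. Local laboratories in a worldwide study make differing units possible. The ban on waivers means that a site cannot settle a borderline case by prior agreement with the sponsor.

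**Working it through.** **Inputs.** From Table 7: 8 g/dL and 5.6 mmol/L. The documents give no conversion factor, so the molar mass M of haemoglobin is an assumption. I use the monomer mass of about 16,114.5 g/mol as the main case, with a range around it.

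**Formula.** mmol/L = g/dL × 10 × 1000 / M, so the factor is 10,000 / M.

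**Attempt to reproduce the printed pair.** In the main case the factor is 10,000 / 16,114.5 = 0.6206.

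- 8 g/dL × 0.6206 = 4.96 mmol/L, not 5.6.
- 5.6 mmol/L / 0.6206 = 9.02 g/dL, not 8.
- The gap is 9.02 − 8 = 1.02 g/dL, or 5.6 − 4.96 = 0.64 mmol/L.

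The pair is not reproduced.

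**Other assumptions about M.**

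| Assumed mass (g/mol) | Factor | 8 g/dL in mmol/L | 5.6 mmol/L in g/dL | Gap (g/dL) |
|---|---|---|---|---|
| 16,000 (monomer, low) | 0.6250 | 5.00 | 8.96 | 0.96 |
| 16,114.5 (monomer, main) | 0.6206 | 4.96 | 9.02 | 1.02 |
| 16,500 (monomer, high) | 0.6061 | 4.85 | 9.24 | 1.24 |
| 64,458 (tetramer) | 0.1551 | 1.24 | 36.1 | 28.1 |

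The tetramer convention would put the limit at about 36 g/dL, which is not physiologically possible. The table must therefore use the monomer convention. For the two values to agree, the factor would have to be 5.6 / 8 = 0.700, or M = 10,000 / 0.700 = 14,286 g/mol. That lies outside every case in the table.

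**Rounding.** If 5.6 is a rounded value, the true figure lies between 5.55 and 5.65 mmol/L, which is 5.55 / 0.6206 = 8.94 to 5.65 / 0.6206 = 9.10 g/dL. Even if 8 stood for as much as 8.49 g/dL, that is only 8.49 × 0.6206 = 5.27 mmol/L. Rounding does not close the gap.

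**Two readings of 'or'.**

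- Each site applies the value in its own unit. A haemoglobin of 8.5 g/dL passes at a g/dL site. The same sample is 8.5 × 0.6206 = 5.28 mmol/L and fails at a mmol/L site.
- Either value is enough. Any result above 5.6 mmol/L is above about 9.0 g/dL and already meets the 8 g/dL limit. The mmol/L value then never decides a case.

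**Population covered.** Arm 1 has 90 planned participants, Arm 2 Part I has 35 (HCC is excluded there by the note to criterion 23), and gastric Cohort E has 30: 90 + 35 + 30 = 155 of 185. The other 30 are Cohort D (HCC), under Table 8.

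**The case against.** The best defence is the literal 'or'. If either limit suffices, a candidate at 8.5 g/dL qualifies everywhere, and a mmol/L site need only convert. The ban on waivers does not say in which unit a site must work. This stands to the extent that unequal treatment by unit is conditional: it follows from the own-unit reading, which is the natural one but is not written down. It does not rescue the cell, because it leaves a printed limit with no function.

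One could also point to the general note on adapting laboratory requirements. That note concerns local regulations and chemotherapy guidelines. It is not a conversion rule, and Appendix 7 (country-specific requirements) does not address haemoglobin limits.

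The defence is stronger on consequences. A reader might infer that fitness at entry, and with it the objective response rate (ORR) and adverse event estimates, will differ by country. The documents do not support that. They do not say that any site reports in mmol/L, they give no haemoglobin distribution, and no analysis by country is specified. Section 9.6.1 reports ORR by arm and cohort with Clopper-Pearson intervals, and the one subgroup named in Section 9.10 concerns non-injected target lesions. A reader might also take 155 as the number affected. It is the planned number to whom Table 7 applies, and the synopsis says that total enrolment may fall short of 185.

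Finally, the amendment summary says that the study is to be discontinued, so correcting the cell may change few or no future enrolment decisions. That stands and limits what the correction can achieve.

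The two limits also carry different inequality signs. This matters only for a result exactly at the limit, and I put no weight on it.

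**Conclusion.** The point holds as an internal numerical contradiction in a mandatory, non-waivable entry criterion. Under every plausible monomer mass the two printed limits differ by about 1 g/dL (0.96 to 1.24 g/dL), and nothing elsewhere in the documents reconciles them. The conversion factor is my assumption, but the conclusion does not depend on its exact value.

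The practical reach is modest. The criterion covers up to 155 of the 185 planned participants. Those who could be classified differently are only those between about 8 and 9 g/dL, and only if a site works in mmol/L and applies that value. Their number is unknown and may be zero. The sample size and the Table 20 confidence intervals are unaffected, and no shift in response or safety estimates is shown. Which of the two limits is intended cannot be determined from the documents: Table 8 shares the g/dL figure but applies to a different population.

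**What to change.** Reconcile the haemoglobin row of Table 7 so that the g/dL and mmol/L values express one threshold. The sponsor decides which threshold was intended.

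Then query baseline haemoglobin, with its reporting unit, for enrolled non-HCC participants between about 8 and 9 g/dL (4.96 to 5.6 mmol/L). Classify their eligibility by one stated rule, so that the same value is not a deviation at one site and acceptable at another. The study report should give the reconciled criterion and, if anyone falls in the band, the number.

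The cost is one table cell and one database query. With the study closing, the benefit lies mainly in consistent deviation classification and an accurate account of the entry criteria.
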